### 5.2.3.3 Dose Confirmation – Arm 2A

The objective of dose confirmation in Part B is to refine the estimate of tolerability of the MK-4280 preliminary RP2D (when delivered in combination with pembrolizumab) based on a TPI design [1] with a target toxicity rate less than or equal to 30%, utilizing the first 14 subjects enrolled in this part in Cohort A, Cohort C, and Cohort D. Dose confirmation involves the expansion of at least 1 dose level studied in the dose-escalation stage of the study. After dosing of the first 14 subjects in Part B, dosing will continue as planned.

The 200 mg dose of pembrolizumab will not be adjusted.

Table 4 Dose Confirmation Rules

Number of Toxicities	Number of Subjects Treated at Current Dose										
	4	5	6	7	8	9	10	11	12	13	14
0	S	E	E	E	E	E	E	E	E	E	E
1	S	S	S	S	S	E	E	E	E	E	E
2	D	S	S	S	S	S	S	S	S	S	S
3	DU	D	D	S	S	S	S	S	S	S	S
4	DU	DU	DU	D	D	D	S	S	S	S	S
5		DU	DU	DU	DU	DU	D	D	S	S	S
6			DU	DU	DU	DU	DU	DU	D	D	D
7				DU	D						
8					DU						
9						DU	DU	DU	DU	DU	DU
10							DU	DU	DU	DU	DU
11								DU	DU	DU	DU
12									DU	DU	DU
13										DU	DU
14											DU

E = Escalate to the next higher dose.  
S = Stay at the current dose.  
D = De-escalate to the next lower dose.  
DU = The current dose is unacceptably toxic.  
Target toxicity rate = 30%.  
Noninformative prior is used: a=1; b=1;  
k1=1; k2=1.5; pow=1 per [1].

Subjects may be enrolled continuously (ie, without waiting for Cycle 1 completion of subjects who have received the first dose) unless a DLT is observed at the particular dose. Once a DLT is observed, the number of subjects who are enrolled at that dose but are not yet fully evaluable for DLT assessment may not exceed the number of remaining subjects who are at risk of developing a DLT before the dose would be considered unacceptably toxic (denoted as DU in Table 4). For example, if 3 of 7 subjects have experienced a DLT at a given dose level, no more than an additional 2 subjects should be enrolled at this dose level until additional DLT data are available. This is because this dose level would be considered unacceptably toxic if all 2 of the additional subjects experience a DLT (ie, 5 of 9 subjects with DLT in Table 4). To find out how many more subjects can be enrolled, one can count

steps in diagonal direction (down and to the right) from the cell (7 subjects, 3 toxicities) to the first cell marked DU.

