#### **5.2.3.4 Dose Confirmation – Arm 3 and Arm 4**

A TPI design will be used to assess the safety and tolerability of MK-4280 and pembrolizumab when administered in combination with either mFOLFOX7 or FOLFIRI and to determine RP2Ds of the triplet combinations, with a target toxicity rate less than or equal to 30%, utilizing the first 14 subjects enrolled in each arm. At the start of each new dose, 3 subjects will be enrolled (with at least 24 hours between each of these 3 subjects) and must complete their DLT evaluation period before additional subjects can be enrolled. Assuming no DLTs in the first 3 subjects have completed their DLT evaluation period, up to 6 subjects at a time can be enrolled and evaluated for DLTs following TPI rules, until 14 subjects are enrolled. If 1 or more DLTs are observed in the first 3 subjects on either cohort, 3 subjects at a time may enroll simultaneously for DLT assessment, until 14 subjects are treated. All other rules regarding the enrollment of subjects and de-escalation of doses are the same as in Section 5.2.3.3 and in [Table 4](#). If the TPI calls for an initial de-escalation, the doses of mFOLFOX7 and/or FOLFIRI will be adjusted as described in [Table 3](#). If this lower dose is still determined to be unacceptably toxic, enrollment into that Arm will be closed. If, after 14 subjects are treated at a particular dose level, the TPI calls for “Stay” (or “Escalate” at the highest dose level), this dose will be considered the RP2D and an additional 6 subjects will be enrolled. Note that the TPI will operate independently for Arm 3 and Arm 4.

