#### **5.2.4 Definition of Dose Limiting Toxicity**

Dose limiting toxicities will be defined from toxicities observed during the first cycle of treatment (21 days) for each dose level. See Section 5.9 for rules on replacement of subjects in the DLT period.

The occurrence of any of the following toxicities during Cycle 1, if assessed by the investigator to be unrelated to the underlying disease, will be considered a DLT:

- Grade 4 non-hematologic toxicity (not laboratory)
- Grade 4 hematologic toxicity lasting at least 7 days, except thrombocytopenia
  - a. Grade 4 thrombocytopenia of any duration
  - b. Grade 3 thrombocytopenia if associated with bleeding
- Grade 3 nonhematologic toxicity (not laboratory) lasting more than 3 days despite optimal supportive care. Grade 3 nausea, vomiting, or diarrhea will be considered a DLT if lasting more than 3 days despite optimal supportive care.

**Arm 6 only:** Excluding Grade 3 hypertension able to be controlled by medication.

- Any Grade 3 or Grade 4 nonhematologic laboratory abnormality, if
  - medical intervention is required, or
  - the abnormality leads to hospitalization, or
  - the abnormality persists for more than 1 week.
- Febrile neutropenia Grade 3 or Grade 4:
  - Grade 3 is defined as absolute neutrophil count (ANC)  $<1000/\text{mm}^3$  with a single temperature of  $>38.3^\circ\text{C}$  ( $101^\circ\text{F}$ ) or a sustained temperature of  $\geq 38^\circ\text{C}$  ( $100.4^\circ\text{F}$ ) for more than 1 hour.
  - Grade 4 is defined as ANC  $<1000/\text{mm}^3$  with a single temperature of  $>38.3^\circ\text{C}$  ( $101^\circ\text{F}$ ) or a sustained temperature of  $\geq 38^\circ\text{C}$  ( $100.4^\circ\text{F}$ ) for more than 1 hour, with life-threatening consequences and urgent intervention indicated.
- Any drug-related AE that caused the subject to discontinue treatment during Cycle 1
- Grade 5 toxicity
- Any treatment-related toxicity that causes a greater than 2-week delay in initiation of Cycle 2

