### 5.2.5 Timing of Dose Administration

Trial treatment may be administered up to 3 days before or 5 days after the scheduled Day 1 of each cycle, beginning in Cycle 3. Cycle 2 Day 1 may be administered up to 5 days after the scheduled Day 1. For Arm 6 only, trial treatment may be administered up to 3 days before or 3 days after the scheduled Day 1 of each cycle, beginning in Cycle 3. Cycle 2 Day 1 may be administered up to 3 days after the scheduled Day 1. In addition, dosing interruptions are permitted in the case of medical / surgical events or logistical reasons not related to study therapy (eg, elective surgery, unrelated medical events, subject vacation, and/or holidays). Subjects should be placed back on study therapy within 2 weeks of the scheduled interruption, unless otherwise discussed with the Sponsor. The reason for interruption should be documented in the subject's study record.

In Arm 2 of Part A and Part B, pembrolizumab will be administered first on Day 1 of each cycle, with administration of MK-4280 occurring approximately 30 minutes after completion of the pembrolizumab administration.

In Arm 3 and Arm 4 of Part B, pembrolizumab will be administered first, with administration of MK-4280 occurring approximately 30 minutes after completion of the pembrolizumab administration. On visits where MK-4280, pembrolizumab, and chemotherapy are to be administered, chemotherapy should be given according to local practice guidelines 30 minutes after completion of the MK-4280 administration.

In Arm 6 of Part B, pembrolizumab will be administered first and then, following a 30-minute interval, MK-4280 will be administered. Lenvatinib will be taken orally with water (with or without food) at approximately the same time each day in 21-day cycles. However, on visit days when pembrolizumab and MK-4280 are also administered, lenvatinib will be administered 0 to 4 hours after the MK-4280 infusion is complete.

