### **8.5 Analysis Populations**

#### **8.5.1 Safety Analysis Populations**

The ASaT population will be used for the analysis of safety data in this study. The ASaT population consists of all subjects who received at least 1 dose of study treatment. In case of treatment administration errors, subjects will be analyzed according to the treatment they actually received. For DLT evaluation, ASaT subjects that were observed for safety for 21 days after the first dose of assigned treatment or experienced a DLT prior to 21 days after the first dose of assigned treatment will be used.

At least 1 laboratory or vital sign measurement obtained subsequent to at least 1 dose of study treatment is required for inclusion in the analysis of each specific parameter. To assess change from baseline, a baseline measurement is also required.

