## 8.9 Sample Size and Power Calculations

### 8.9.1 Dose Escalation and Dose Confirmation

The primary purpose of the dose-escalation and dose-confirmation parts of the trial is to investigate the safety and tolerability of MK-4280 monotherapy, MK-4280 in combination with pembrolizumab, and MK-4280 in combination with pembrolizumab and either mFOLFOX7, FOLFIRI or lenvatinib in adult subjects with advanced solid tumors (Part A and first 14 subjects in the PD-1-treatment-naïve HNSCC and CRC cohorts in Part B Arm 2A, and Arm 3, Arm 4 and Arm 6 in Part B) and to establish RP2Ds for MK-4280 in combination with pembrolizumab and in combination with pembrolizumab and either mFOLFOX7, FOLFIRI or lenvatinib.

The final number of subjects enrolled in the dose-escalation and dose-confirmation parts of the study will depend on the empirical safety (DLT) observations, in particular, at what dose the 3+3 design is triggered and what dose is identified as the preliminary RP2D. Sample sizes for a few possible scenarios as well as the estimated time required to enroll all subjects and the time required to determine the preliminary RP2D are provided below. The time required to estimate the preliminary RP2D is the time from the first subject's first dose to the end of the 3-week observation period following the first dose of the last subject enrolled in the dose confirmation part. The study duration is derived as the time from the first subject's first dose to the end of 2-year treatment period following the enrollment of the last Part B subject.

Scenario 1. No DLTs during Part A. For MK-4280, in a scenario where no DLTs are encountered during the dose escalation and dose confirmation parts so that Part A continues to the highest dose in [Table 3](#) for both arms, the sample size to determine the preliminary RP2D is 44 subjects (15 in each of the 2 arms of Part A and the first 14 subjects enrolled in Part B Arm 2A who are dosed via the TPI design).

It will take a minimum of 21 weeks to enroll and observe for DLTs in MK-4280 monotherapy and combination subjects in Part A. Total follow-up for the Part A, Arm 2 subjects treated with pembrolizumab would be 104 weeks plus an additional 90 days to observe subjects with SAEs. The duration for Part A, then, is approximately 125 weeks or slightly greater than 2 ½ years.

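### One DLT criterion (Cycle 2 delayed by more than 2 weeks) cannot be established before Day 37, but subjects become DLT-evaluable at Day 21, so interim TPI decisions can rest on an under-count

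*Combined protocol and SAP*

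**What the plan says.** Section 5.2.4 sets the window: "Dose limiting toxicities will be defined from toxicities observed during the first cycle of treatment (21 days) for each dose level". The same list includes "Any treatment-related toxicity that causes a greater than 2-week delay in initiation of Cycle 2".

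The other sections use 21 days:

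- Section 8.5.1 bases DLT evaluation on "ASaT subjects that were observed for safety for 21 days after the first dose of assigned treatment or experienced a DLT" before that point.
- Section 8.9.1 treats the preliminary RP2D as determined at "the end of the 3-week observation period following the first dose of the last subject enrolled in the dose confirmation part".
- Section 5.2.3.4 says that the first 3 subjects at each new dose of Arms 3 and 4 "must complete their DLT evaluation period before additional subjects can be enrolled". Section 5.2.3.5 says the same for Arm 6. With no DLT among those 3, up to 6 subjects may then be enrolled at a time; with one or more, 3 at a time. Neither section extends the DLT evaluation period beyond 21 days.
- Section 5.2.5 allows some slack: "Cycle 2 Day 1 may be administered up to 5 days after the scheduled Day 1", or 3 days after in Arm 6.

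Section 5.2.3.3 has a rule for pending subjects, which Sections 5.2.3.4 and 5.2.3.5 adopt. Once a DLT has been seen, "the number of subjects who are enrolled at that dose but are not yet fully evaluable for DLT assessment may not exceed" the number still at risk before the dose reaches DU. It does not define full evaluability. Section 5.9 does not list a subject on a Cycle 2 hold among the nonevaluable.

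**The concern.** The criterion needs about two weeks more follow-up than the evaluability rule allows. It matters for a subject with a treatment-related toxicity that falls short of every other DLT criterion but stops Cycle 2 from starting. At Day 21 that subject has completed the observation period and has no DLT on record. If the Table 4 decision is taken then, the subject counts in the denominator but not in the numerator.

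Three decisions are exposed: whether the next batch is 3 or up to 6, whether the dose stays or is reduced, and whether the dose is declared the RP2D after 14 subjects. In Arms 3 and 4 that last call releases a further 6 subjects; in Arm 6 it releases the rest of the cohort.

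**Working it through.** **1. The window the plan uses.** Section 8.9.1 gives at least 21 weeks to enroll and observe for DLTs in Part A. Section 5.2.1 starts Arm 2 after one cycle at two Arm 1 dose levels, and Table 3 lists five Arm 2 levels. At 3 weeks per level, (2 + 5) × 3 = 21 weeks. The figure reproduces exactly with a 21-day window and no time for a Cycle 2 hold.

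**2. When the criterion can be met.** Cycle 2 Day 1 is due on Day 1 + 21 = 22. A 2-week delay runs to Day 22 + 14 = 36, so a longer one is first established on Day 37. Counted from the end of the Section 5.2.5 dosing window, it is Day 22 + 5 + 15 = 42, or Day 22 + 3 + 15 = 40 in Arm 6.

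**3. What one unresolved subject can change in Table 4.**

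| Subjects | Full count | One fewer |
|---|---|---|
| 6 | 3: D | 2: S |
| 9 | 4: D | 3: S |
| 11 | 5: D | 4: S |
| 14 | 6: D | 5: S |

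If the only DLT among the first 3 subjects is unresolved, the next batch can also be up to 6 instead of 3.

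**4. Chance of D or DU at nine subjects under the batch rules.** Let p be the true DLT rate, s the share of DLTs that are delay-only, and q = p(1 − s) the rate visible at Day 21. Table 4 calls D or DU at nine subjects for 4 or more DLTs.

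Among the first 3 subjects, let k be the DLTs visible at Day 21 and d the delay-only DLTs. The pair (k, d) is multinomial with probabilities q, p − q and 1 − p for the remainder. When the last batch reaches Day 21, the batch before it is at about Day 42. That is past Day 37, so earlier batches count at the full rate p and only the last batch counts at q:

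- k = 0: the next batch is 6, and D or DU needs d + Bin(6, q) ≥ 4.
- k ≥ 1: the next batches are 3 and 3, and D or DU needs k + d + Bin(3, p) + Bin(3, q) ≥ 4.

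Summing over (k, d):

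| True rate p | Full count | s = 10% | s = 20% | s = 30% |
|---|---|---|---|---|
| 30% (q = 0.27, 0.24, 0.21) | 27% | 24% | 22% | 19% |
| 40% (q = 0.36, 0.32, 0.28) | 52% | 48% | 43% | 39% |

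This is a single look at nine subjects and ignores any earlier de-escalation. Delay is counted from the scheduled Day 22.

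**5. The call at 14 subjects.** Take the larger-batch path 3 + 6 + 5, with only the last 5 unresolved. The chance of 5 or fewer counted DLTs is P(Bin(9, p) + Bin(5, q) ≤ 5). At p = 40% it is 0.49 with full counting and 0.53 to 0.62 for s from 10% to 30%. Batches of 3 leave fewer subjects unresolved, so the effect is smaller on that path.

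**The case against.** No passage says that held subjects are DLT-free. Section 8.5.1 defines who is in the DLT analysis and does not freeze a subject's status at Day 21. The 3 weeks in Section 8.9.1 is a planning timeline. Full evaluability in Section 5.2.3.3 is undefined, so a held subject could be read as pending. That section also lets the next lower dose be expanded at 5 or fewer of 14 if there is a safety concern. Section 7.1.2.1 has the sponsor and investigators following individual subjects in an open-label trial, so a hold would be visible to them.

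Much of this stands. The under-count is implied, not stated, and a careful team could avoid it. But the pending cap starts only after a DLT has been observed, does not name held subjects, and so may not apply when the unresolved case is the first. The other safeguards are discretionary.

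A reader might infer three stronger things that the documents do not support:

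- **The DLT is lost for good.** Nothing prevents its being counted later. The exposure is in decisions taken meanwhile.
- **All nine subjects are unresolved at the nine-subject look.** With p = 30%, that would put the chance of D or DU at 20%, 15% or 10%. Under the batch rules the earlier batches are already resolved, so the loss is about half that.
- **The chemotherapy arms are most affected.** Table 3 gives chemotherapy on Days 1 and 15 of odd cycles and Day 8 of even cycles, so none is due on Cycle 2 Day 1. Section 5.2.6 allows one agent to be held without the others, although it also allows them to be delayed together. The documents do not show where such delays would be most frequent.

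**Conclusion.** The inconsistency is in the text and should be resolved. A DLT criterion that cannot be judged before Day 37 sits beside a 21-day window, a 21-day evaluability point and enrollment gates tied to that period. Following the rules as written can put an unresolved subject into Table 4 without a DLT.

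The effect on the nine-subject decision is moderate: about 3 to 8 percentage points (27 − 24 to 27 − 19) at a true rate of 30%, and 4 to 13 points (52 − 48 to 52 − 39) at 40%. These sizes rest on the assumed 10% to 30% delay-only share, on batches opening as soon as Day 21 is complete, and on no informal allowance for holds.

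The point concerns only subjects held for treatment-related toxicity who met no other Cycle 1 criterion; a subject who starts Cycle 2 on time is resolved on Day 22. It has no consequence for Part A, which Section 4.2.2.2 reports as fully enrolled and through its DLT period with no DLTs.

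**What to change.** Reconcile Sections 5.2.3.3 to 5.2.3.5, 5.2.4, 5.9, 8.5.1 and 8.9.1 so that the DLT-evaluability point agrees with the protocol's own Cycle 2 delay criterion. State explicitly that a subject whose status on that criterion is unresolved is not entered in Table 4 as DLT-free, and say whether such a subject falls under the Section 5.2.3.3 cap on subjects not yet fully evaluable. State also whether delay is counted from the scheduled Day 22 or from the end of the Section 5.2.5 window.

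This changes wording and counting only: no dose, threshold or DLT criterion is altered. The cost is a wait of up to about 2 weeks before a batch or dose decision, only when a subject is on hold.

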### 5.2.5 Timing of Dose Administration

Trial treatment may be administered up to 3 days before or 5 days after the scheduled Day 1 of each cycle, beginning in Cycle 3. Cycle 2 Day 1 may be administered up to 5 days after the scheduled Day 1. For Arm 6 only, trial treatment may be administered up to 3 days before or 3 days after the scheduled Day 1 of each cycle, beginning in Cycle 3. Cycle 2 Day 1 may be administered up to 3 days after the scheduled Day 1. In addition, dosing interruptions are permitted in the case of medical / surgical events or logistical reasons not related to study therapy (eg, elective surgery, unrelated medical events, subject vacation, and/or holidays). Subjects should be placed back on study therapy within 2 weeks of the scheduled interruption, unless otherwise discussed with the Sponsor. The reason for interruption should be documented in the subject's study record.

In Arm 2 of Part A and Part B, pembrolizumab will be administered first on Day 1 of each cycle, with administration of MK-4280 occurring approximately 30 minutes after completion of the pembrolizumab administration.

In Arm 3 and Arm 4 of Part B, pembrolizumab will be administered first, with administration of MK-4280 occurring approximately 30 minutes after completion of the pembrolizumab administration. On visits where MK-4280, pembrolizumab, and chemotherapy are to be administered, chemotherapy should be given according to local practice guidelines 30 minutes after completion of the MK-4280 administration.

In Arm 6 of Part B, pembrolizumab will be administered first and then, following a 30-minute interval, MK-4280 will be administered. Lenvatinib will be taken orally with water (with or without food) at approximately the same time each day in 21-day cycles. However, on visit days when pembrolizumab and MK-4280 are also administered, lenvatinib will be administered 0 to 4 hours after the MK-4280 infusion is complete.

### 5.2.6 Dose Modification (Escalation/Titration/Other)

CTCAE Version 4.0 must be used to grade the severity of adverse events. If appropriate, the investigator may attribute each toxicity event to MK-4280, pembrolizumab, mFOLFOX7, FOLFIRI, or lenvatinib alone, or to any combination of these agents, and follow the dose modification guidelines accordingly in [Table 5](#), Section 5.2.6.2, and [Table 7](#). If a dose modification for toxicity occurs with any agent, the dose may not be re-escalated in that subject. Dose modifications are always based on the previous cycle.

For Part A, subjects may have 1 dose modification to MK-4280 throughout the course of the study. If further toxicity occurs or the criteria for resuming treatment are not met, the subject must be discontinued from the agent. If a subject experiences several toxicities and there are conflicting recommendations, following the most conservative dose adjustment is recommended (dose reduction appropriate to the most severe toxicity). For Part B, no dose reductions of MK-4280, pembrolizumab, or MK-4280A are permitted.

Reduction or holding of 1 agent and not the other agents is appropriate if, in the opinion of the investigator, the toxicity is clearly related to 1 of the study drugs. However for subject convenience in Arm 2, Arm 3, and Arm 4 (and crossover treatment), if 1 drug is delayed then the other drug(s) can be delayed until they can be administered. If, in the opinion of the

investigator, the toxicity is related to a combination of agents, both drugs should be held according to recommended dose modifications.

For Arm 6, subjects who interrupt or discontinue one or more drug(s) in the lenvatinib plus pembrolizumab plus MK-4280 combination due to toxicity can continue with the other drug(s) in the combination until criteria for treatment discontinuation are met (eg, unacceptable toxicity, disease progression).

Refer to Section 5.2.6.4 for dose modification guidance for overlapping toxicity for the lenvatinib plus pembrolizumab plus MK-4280 combination.

Exceptional circumstances to following the dose modification tables below may be considered after consultation with the Sponsor.

### **5.2.6.1 Immune-Related Events and Dose Modification (Withhold, Treat, Discontinue)**

#### **Dose Modification and Toxicity Management for Immune-related AEs Associated with Pembrolizumab Monotherapy, Coformulations or IO Combinations**

AEs associated with pembrolizumab monotherapy, coformulation, or IO combination exposure may represent an immune-related response. These irAEs may occur shortly after the first dose or several months after the last dose of pembrolizumab monotherapy, coformulation, or IO combination treatment and may affect more than one body system simultaneously. Therefore, early recognition and initiation of treatment is critical to reduce complications. Based on existing clinical study data, most irAEs were reversible and could be managed with interruptions of pembrolizumab monotherapy, coformulation, or IO combination administration of corticosteroids and/or other supportive care. For suspected irAEs, ensure adequate evaluation to confirm etiology or exclude other causes. Additional procedures or tests such as bronchoscopy, endoscopy, skin biopsy may be included as part of the evaluation.

